#### A. DEFINITIONS

The IRB represent an oversight body, constituted of GNF employees and external board members, charged with overseeing certain activities at GNF. Activities under IRB oversight, include all activities relating to the performance of assisted reproduction (i.e., in vitro fertilization and related procedures) and all research activities at GNF.

Moreover, the IRB shall serve as GNF's human subject and ethical advisory board, which shall be consulted by GNF staff whenever ethical issues arise, which are not clearly defined by the standard of daily clinical care, practiced at GNF and in the community.

IRB members are subject to annual appointments and re-appointments by the ART Director or designee of GNF.

There shall be no payments made to IRB members, though they may receive reimbursement for expenses incurred in fulfillment of their responsibilities as IRB members.

While IRB members are subject to appointment by the ART Director or designee of GNF, the IRB shall be representative of GNF as well as general community interests. Therefore, the position of Chair shall be filled by an external (non-GNF employed) individual, who shall be either a physician or scientist and, preferably, a majority of board members shall be representative of community interests (i.e., be external board members). The ART Director or designee of GNF shall serve as Vice-Chair of the IRB.

The IRB shall in all of its functions report directly to the Board of Directors of GNF. While the ART Director or designee of GNF appoints IRB members, involuntary dismissal of IRB members shall only be possible by decision of the Board of Directors of GNF.

Since members of the IRB may have access to confidential patient data, they shall be obliged to sign a confidentiality agreement with GNF, which mandates that all patient information they become privy to be held in confidence and not be communicated to any third parties.

#### B. MISSION STATEMENT:

The mission of GNF's IRB is to assure that all clinical and research activities, conducted at GNF, comply with basic human rights, as defined by the revised Declaration of Helsinki, passed in October 2000 at the 52nd World Medical Association General Assembly in Edinburgh, Scotland, UK and that any form of animal experimentation, if conducted at

GNF, follows internationally accepted guidelines for the protection of animals in such research.

#### **C. PROCESS IMPLEMENTATION:**

All application forms, required for submission to the IRB, shall be electronically available from the business offices of GNF.

The IRB shall meet per need, as defined by Chair or Vice-Chair. A quorum is defined as the presence of at least one third of appointed members.

Meetings of the IRB shall follow rules and shall be documented by minutes, to be signed by Chair or Vice-Chair.

Agenda and items, submitted for review to any IRB meeting, shall be distributed to all IRB members at least five (5) working days in advance of such meeting to allow for proper familiarization with materials.

Each research project, submitted for review to the IRB, shall be numbered with date of IRB meeting when first reviewed and consecutive project number of that meeting (i.e., for example 8/21/19-1, denoting the first project reviewed by the IRB on 8/21/19).

The principal investigator (PI) for each research project shall be principally responsible for annual progress and/or completion reports.

GNF's manager shall maintain all IRB files and shall inform Chair of IRB in timely fashion of annual and/or completion reports that become due.

Items submitted for review by the IRB may be of the following nature:

##### **(i) INFORMAL REPORT:**

Purpose: Information of IRB members only; no decision expected/required.

Examples: IVF-related outcome reports, or informal updates on previously approved research projects.

##### **(ii) INQUIRY:**

Purpose: Question to IRB;

Examples: Ethical concerns or introduction of ethically controversial new clinical technique in IVF.

##### **(iii) NEW RESEARCH PROJECT:**

Purpose: Review and approval;

##### **(iv) EXPEDITED REVIEW:**

Purpose: Expedited review and approval by Chair alone.

##### **(v) RE-APPROVAL/TERMINATION OF RESEARCH PROJECT**

Purpose: Re-approval or termination;

Requests for IRB involvement in regards to (i), (ii) and (v) shall take the format of a formal letter "to the IRB".

Requests for IRB involvement in regards to (iii) shall take the format of a formal research project review, using standard GNF IRB format (Appendix), including a covering letter by the principal investigator (PI) "to the IRB," requesting review and approval of the proposed project.

Requests for IRB involvement in regards to (iv) shall take the format of a formal letter from the PI "to the IRB," requesting expedited review and approval of a project by the Chair.

Such a letter shall contain: (1) a description of reason(s) why expedited (in place of full IRB) review appears appropriate (see below); (2) documentation by supporting documents (i.e., prior IRB approvals of project at other institution, etc).

#### CRITERIA FOR EXPEDITED REVIEW

All research shall be reviewed by the full IRB unless criteria for expedited review of a project are met, in which case only the Chair, under his full discretion, can choose to grant expedited review and approval. The Chair, at own discretion, can at any moment return such expedited review to review by the complete IRB.

In case the Chair grants expedited review and approves a project, he shall issue a formal written approval letter for the project, which shall otherwise administratively be handled like any other research project, reviewed by the IRB, with the date of the decision letter being considered the date of IRB review.

Criteria for expedited review exist if:

- (i) A research project has previously undergone detailed review and approval at another formal IRB and such process is documented.
- (ii) GNF joins a research project, already elsewhere underway, and at that other institution reviewed and approved by a formal IRB.
- (iii) Another institutions wishes to join a GNF project, already previously reviewed and approved by GNF's IRB.
- (iv) The complete IRB has granted the Chair specific authority.

#### APPENDIX

#### SUBMISSION PACKAGE, REQUESTING REVIEW

#### AND CONSIDERATION FOR APPROVAL OF

#### RESEARCH PROJECT BY GNF's IRB

EXPEDITED REVIEW

New Research Project

COMPLETE APPLICATION

#### IVF AND PRP HISTORICAL CONTEXT

In vitro fertilization (IVF) was first successfully employed in a human in 1978 during an unstimulated natural cycle, leading to the birth of Louise Brown, the first IVF baby. Due to the limited success of natural IVF cycles, gonadotropins were introduced as a means to stimulate the growth and maturation of multiple antral follicles before oocyte retrieval, significantly improving the efficiency of IVF treatments. Over the years, controlled ovarian stimulation has enhanced the success of IVF by increasing the number of mature oocytes retrieved, thereby improving fertilization rates and the likelihood of achieving pregnancy and live birth.

Autologous platelet-rich plasma (PRP) was introduced as a transfusion product by hematologists in the 1970s for the treatment of thrombocytopenia. PRP is defined as plasma with a platelet concentration above that of peripheral blood and has since been widely adopted in various medical fields, including orthopedics, cardiothoracic surgery, plastic surgery, dermatology, dentistry, and diabetic wound healing, due to its regenerative properties.

The first recorded ovarian PRP (oPRP) procedure was performed in 2018, demonstrating improvements in ovarian function, folliculogenesis, and ovulation induction, particularly in patients with diminished ovarian reserve. Preliminary studies have suggested that oPRP injections may enhance ovarian reserve markers, increase the number of retrieved mature oocytes, and improve embryo quality, leading to better IVF outcomes. The mechanism behind oPRP's efficacy is believed to involve growth factors such as platelet-derived growth factor (PDGF), transforming growth factor-beta (TGF- $\beta$ ), and vascular endothelial growth factor (VEGF), which contribute to tissue regeneration and angiogenesis within the ovarian microenvironment.

The potential benefits of PRP for ovarian and endometrial rejuvenation have been postulated based on data extrapolated from prior medical research. However, despite promising initial findings, most of the information demonstrating the benefit of PRP on ovarian reserve, oocyte quality, and embryo development remains limited to anecdotal evidence and small-scale studies. Large-scale, well-controlled clinical trials are needed to establish definitive efficacy and safety in this domain.

#### PURPOSE OF THIS RESEARCH

This is a non-randomized prospective self-controlled interventional study evaluating the impact of oPRP injections on embryo quality in patients undergoing two IVF cycles.

Participants will undergo two IVF cycles at Generation Next Fertility.

The first cycle will serve as the control (no oPRP treatment), while the second study cycle will incorporate oPRP injections.

Oocytes retrieved will undergo fertilization using one of the following methods:

Conventional Insemination

Intracytoplasmic sperm injection (ICSI)

ICSI with Zymot

ICSI with Zymot and Physiological ICSI (PICSI)

Patients may opt for Preimplantation Genetic Testing for Aneuploidy (PGT-A) through Genomic Prediction LLC's LifeView™ platform, which utilizes single nucleotide polymorphism (SNP) technology to enhance accuracy in detecting chromosomal abnormalities.

All embryos from both IVF cycles will be cultured in a time-lapse incubators for automated tracking and assessment.

Embryo quality will be measured by an AI software used in conjunction with the time-lapse incubators.

This study aims to evaluate whether ovarian platelet-rich plasma (oPRP) injections improve embryo quality in In Vitro Fertilization (IVF) cycles. Patients will undergo two IVF cycles:

First cycle (Control cycle): A standard IVF cycle with individualized ovarian stimulation protocols based on AMH, AFC and patient history and prior IVF outcomes when applicable.

Second cycle (Study cycle): Includes oPRP injections, administered:

1-2 weeks after the onset of menses following the first IVF cycle.

A second injection between stimulation days 2-5 of the second IVF cycle.

The protocol of the second IVF cycle will be again based on the same criteria as the first IVF cycle. Embryos from both cycles will be monitored using a time-lapse incubator in conjunction with an AI software to analyze embryo development and assess Embryo Quality (EQ) scores. The study will determine if oPRP improves embryo quality and implantation potential. Each embryo will be given an EQ (embryo quality) score based on the morphokinetics of the embryos during the incubation period. The Embryo Quality (EQ) Score, generated through AI analysis, will be used to assess whether oPRP improves embryo development, viability, and implantation potential. No clinical decision will be made based upon the resulting Embryo Quality (EQ) Score. The time-lapse based AI software for embryo assessment is an investigational device, which means that it is not approved by the Food and Drug Administration (FDA)

## STUDY PROTOCOL

### 1. Baseline Evaluation & Enrollment

All participants will undergo a baseline ultrasound and hormonal blood workup at the start of their menstrual cycle, approximately one month or more prior to initiating the first IVF cycle. This baseline assessment will include:

Ultrasound to determine antral follicle count (AFC) and assess ovarian morphology.

Hormonal testing including Anti-Müllerian Hormone (AMH), Follicle-Stimulating Hormone (FSH), Luteinizing Hormone (LH), Estradiol (E2), Progesterone (P4), Thyroid Stimulating Hormone (TSH), Prolactin (PRL) and Beta-Human Chorionic Gonadotropin ( $\beta$ -hCG).

Routine infectious disease screening in compliance with IVF laboratory standards for both the patient and any male partner.

Genetic Carrier screening through Horizon™ advanced carrier screening test by Natera, Inc. will be offered to all patient's and their partners

Semen Analysis for all male partners to determine if a male factor infertility is present.

Patients will then proceed with their first IVF cycle under a standardized ovarian

stimulation protocol based on their ovarian reserve and history of previous IVF response when applicable.

## 2. First IVF Cycle (Control)

The first IVF cycle will serve as a control cycle, conducted without oPRP injections.

The ovarian stimulation protocol (natural, mild, or conventional) will be determined based on AFC and hormonal profile.

Once the lead follicle reaches the appropriate size ( $\geq 18$  mm), ovulation will be induced using 10,000 IU of human chorionic gonadotropin (hCG) or 250 mcg Ovidrel®, or 80-100 IU of Leuprolide acetate or a combination of the above administered approximately 35.5 hours prior to retrieval.

Oocyte retrieval will be performed under deep intravenous (IV) sedation by a board-certified anesthesiologist, using transvaginal ultrasound guidance.

Fertilization Method Options:

Conventional Insemination

Intracytoplasmic sperm injection (ICSI)

ICSI + Zymot sperm selection

ICSI + Zymot + Physiological ICSI (PICSI)

With or without PGT-A using SNP-based LifeView® technology from Genomic Prediction LLC.

Up to 15 embryos will be cultured in the time-lapse incubator, which in conjunction with AI, provides an automated embryo quality score based on morphokinetic parameters. The resulting AI Score will not be used to guide any clinical decisions.

All embryos reaching the blastocyst stage will be biopsied (if PGT-A is elected), vitrified, and stored for potential future embryo transfer.

## 3. oPRP Treatment & Second IVF Cycle (Study Cycle)

Following the first IVF cycle, patients will undergo their first oPRP injection:

Timing: 1-2 weeks after the onset of the next menstrual cycle.

Procedure: Under IV sedation, a patient's autologous PRP will be prepared and injected directly into both ovaries under transvaginal ultrasound guidance.

Second IVF Cycle (oPRP Study Cycle)

The same ovarian stimulation protocol will be used for consistency.

A second oPRP injection will be performed on stimulation days 2-5 to enhance folliculogenesis.

Ovulation will be triggered at the same follicular size thresholds, and oocyte retrieval will follow identical protocols.

Fertilization methodology will be identical to the first cycle unless no fertilization is identified in the first cycle.

Embryo Development Analysis: Up to 15 embryos will be cultured in a time-lapse incubator, which in conjunction with AI, provides an automated embryo quality score based on morphokinetic parameters. The resulting AI Score will not be used to guide any clinical decisions.

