### **Secondary Outcome Measures:**

Improvement in embryo quality based on Morphokinetics using the AI score from time-lapse videography.

Changes in ovarian reserve markers (AMH, AFC, FSH, E2) post-oPRP.

Increase in the number of mature (MII) oocytes retrieved in the second IVF cycle.

Increase in 2 PN embryos formed

Increase in Day 3 embryos formed with 6 cells or more

Increase in Blastocysts formed

Increase in High Quality blastocysts formed (3BB or better)

Increase in Euploid embryos based on PGT-A analysis when available

Clinical pregnancy rate per embryo transfer.

Live birth rate following embryo transfer.

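### The protocol gives two rules for choosing cycle 2 stimulation, and one of them would let a stimulation change be counted as an oPRP effect

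*Protocol*

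**What the plan says.** All references are to the Protocol.

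- **Purpose of this Research, cycle 1.** Stimulation follows "individualized ovarian stimulation protocols based on AMH, AFC and patient history and prior IVF outcomes when applicable".
- **Purpose of this Research, cycle 2.** "The protocol of the second IVF cycle will be again based on the same criteria as the first IVF cycle".
- **Section 1 (Baseline Evaluation & Enrollment).** AMH, AFC and the other hormones are measured before the first cycle. Cycle 1 stimulation depends on ovarian reserve and on any earlier IVF response.
- **Section 2 (First IVF Cycle).** "The ovarian stimulation protocol (natural, mild, or conventional) will be determined based on AFC and hormonal profile".
- **Section 3 (oPRP Treatment & Second IVF Cycle).** "The same ovarian stimulation protocol will be used for consistency". No exception is given for stimulation. The fertilization method is also held fixed, with one stated exception: failed fertilization in cycle 1.
- **Timing of the first oPRP injection (Purpose of this Research).** "1-2 weeks after the onset of menses following the first IVF cycle", so before cycle 2 stimulation starts.
- **Secondary Outcome Measures.** These include "Changes in ovarian reserve markers (AMH, AFC, FSH, E2) post-oPRP" and "Increase in the number of mature (MII) oocytes retrieved in the second IVF cycle".
- **Number of Subjects / Length of Participation.** Each patient is her own control. The section acknowledges time-dependent confounding in general terms and says an external two-cycle group without oPRP will be considered.

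**The concern.** The trial estimates the oPRP effect as cycle 2 minus cycle 1 within patients. The order is fixed, no randomized arm runs alongside, and the external group is not a firm commitment. Whatever else differs systematically between the cycles is therefore part of the estimate. Stimulation is the main co-treatment in an IVF cycle, and the protocol's own background says that "controlled ovarian stimulation has enhanced the success of IVF by increasing the number of mature oocytes retrieved".

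If stimulation may be chosen afresh for cycle 2, the paired difference describes oPRP plus re-chosen stimulation. The choice could also respond to the control-cycle result, so the patients whose regimen changes could be those whose control cycle went badly. Two clinicians could treat similar patients differently, each citing a sentence of the protocol, and neither would have a deviation to record. An analysis cannot restore a regimen that has already been changed. Adjusting for a choice made on post-oPRP markers would mean adjusting for something oPRP may have affected.

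**Working it through.** The plan states no figure on this point, so the check compares the texts and then works out what follows for the estimate.

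**1. Do the two rules say the same thing?** Section 3 carries the regimen over. The Purpose section carries the criteria over and says the protocol will again be based on them. The rules agree only if every criterion has the same value at both cycles.

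**2. Can the criteria change between cycles?**

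| Criterion for cycle 1 | Status at cycle 2 |
|---|---|
| Prior IVF outcomes | Include the control cycle for every patient who reaches cycle 2 |
| AMH, AFC | Unchanged if the section 1 baseline values are reused; post-oPRP if taken at the start of cycle 2 |
| Patient history | Could be read to include the control cycle |

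The first row follows directly from the wording. The second is only a permitted reading: no text schedules a new AMH or AFC in order to choose cycle 2 stimulation. However, the reserve markers are to be assessed after oPRP as an outcome, and no text freezes the criteria at baseline.

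**3. How far could the regimen move?** Section 2 names three classes: natural, mild and conventional. A move between classes would be allowed under the Purpose sentence read as a fresh choice. Section 3 would not allow it.

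**4. What would that do to the estimate?** Let *s* be the share of patients whose stimulation changes and *d* the mean shift in the outcome in those patients caused by the change. Then

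bias in the mean paired difference = *s* × *d*.

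If section 3 is followed, *s* = 0 and the bias is 0. Otherwise, as *s* lies between 0 and 1, the bias lies between 0 and *d*. The protocol gives neither *s* nor *d*, so neither the size nor the sign can be derived.

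**5. Which outcomes are exposed?** The ten secondary outcomes are: (1) AI embryo score, (2) reserve markers, (3) MII oocytes, (4) 2PN embryos, (5) day 3 embryos with at least 6 cells, (6) blastocysts, (7) high-quality blastocysts, (8) euploid embryos, (9) clinical pregnancy, (10) live birth.

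- Items 3 to 8 are worded as increases in oocytes or embryos: 8 − 3 + 1 = 6 of 10. For item 3, the background section itself says that stimulation raises the number.
- Item 2 contains AMH and AFC, which are also criteria for choosing stimulation. This is an overlap of input and outcome; the document does not show that a stimulation change would bias these markers.
- The primary outcome is a blastocyst formation rate, and the sample size section takes it per oocyte retrieved. Stimulation acts on that denominator, but the document gives no direction or size for the rate.

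**The case against.** The strongest reply is that section 3 settles the matter. It is the procedural section, it is specific to cycle 2, it gives its reason, and it sits among other provisions that hold trigger thresholds, retrieval and fertilization constant. Where a departure was wanted, one was written in. The Purpose sentence is overview text and may mean only that the same basis leads to the same protocol. On this view the wording is loose and nothing would happen in practice.

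Three further points are fair:

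- The post-oPRP marker route is inferred, since baseline testing is scheduled only before cycle 1.
- A count of exposed endpoints is not a measure of bias.
- The primary rate is not shown to move.

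These last three stand as limits on the concern. The main reply does not remove the conflict. Section 3 is the better rule, but the document does not rank the two sentences, and the benign reading needs criteria frozen at baseline, which no text states. The control-cycle route needs no new measurement: prior IVF outcomes are a listed criterion, and the control cycle is one by then. The general acknowledgement of time-dependent confounding does not cover a co-treatment change that the investigator chooses and could avoid.

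**Conclusion.** The concern holds, and the text should be fixed. The protocol contains two rules for cycle 2 stimulation that can lead to different treatment, and following one of them as written would allow an avoidable confounder into a fixed-order paired comparison.

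The size is unknown: zero under section 3, and otherwise the share of patients changed times the mean shift, neither of which the protocol gives. The exposure is clearest for the six count-type secondary outcomes. No effect on the primary rate is claimed in either direction. The conclusion assumes that the Purpose sentence can reasonably be read as a fresh choice. It does not depend on AMH or AFC being re-measured. Confidence is high that the two rules conflict; nothing is claimed about how often staff would follow the looser one.

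**What to change.** Let section 3 govern and replace the Purpose sentence with wording such as: *Cycle 2 repeats the cycle 1 stimulation regimen (Study Protocol, section 3). Deviations are allowed only for safety and are recorded with the reason.* Leave the fertilization exception in section 3 as it is.

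It would help to say in section 3 what is carried over: the class (natural, mild or conventional), drugs, starting dose and trigger. Without that, changes within a class could continue under the same label.

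The cost is one amended sentence, the short definition if adopted, and a recorded reason for each deviation. The safety allowance is new wording, but it loosens section 3, which has no exception for stimulation. The clinical downside is that stimulation cannot be re-optimised after a poor control cycle, which section 3 already implies. The change does not remove confounding from the fixed order of cycles; it only keeps a co-treatment change from being added to it.
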